- ^f A full C-SSRS assessment will be performed only when study participant has a positive response to Question 1 of the suicidal ideation query. If a study participant has active suicidal ideation as confirmed by the answer 'Yes' to Question 4 or Question 5 of the C-SSRS assessments, the study participant will be excluded or withdrawn from the study and immediately referred to a Mental Healthcare Professional.
- ^g Chest X-ray should only be performed at sites in countries at high risk for TB (see Section 8.2.6). If chest X-ray is performed, the study participant cannot be dosed until the result is available, and negative.
- ^h The IGRA test will be performed in a central laboratory. Study participant should not be dosed in case of any positive IGRA or two indeterminate IGRAs until the study participants has been evaluated by a TB specialist.
- ⁱ Urine pregnancy test will be performed using a dipstick test; a positive urine pregnancy test must be confirmed using a serum pregnancy test.
- ^j Study participants must be observed at site postdose for at least 4 hours following the first 2 infusions, and then 2 hours thereafter for subsequent infusions.
- ^k At dosing visits, PK samples should be taken predose for all study participants.
- ^l Additional exploratory safety samples must be collected 4 hours postdose or as soon as possible before the next IMP in case of AESM of severe headache and/or AESM of severe GI disorders as described in Section 8.3.7.
- ^m MuSK and AChR antibodies will be tested at Baseline. All subsequent testing will be limited to the positive antibody.
- ⁿ To be collected predose at V2, and 4 hours postdose at V9. Additional samples should be collected 2 hours and 4 hours postevent or as soon as possible before the next IMP for study participants with severe headache and/or infusion reaction or hypersensitivity reaction.
- ^o MGII is optional for all study participants.

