2.3 Benefit/Risk Assessment

Generalized myasthenia gravis (gMG) is a rare, debilitating, chronic autoimmune disease driven by, in large part, IgG autoantibodies that target neuromuscular junctions (NMJs). Most current treatment approaches are not targeted treatments to the specific underlying pathology of IgG

autoantibody formation. Rather, they produce a broad cascade of immune suppression, which results in undesirable side effects such as those seen with high-dose chronic steroid use. Many treatments of choice often require invasive, expensive and time-consuming inpatient procedures such as PEX, or intravenous administration of immunoglobulins at a healthcare facility.

Rozanolixizumab represents an innovative, subcutaneous anti-FcRn monoclonal antibody that may provide a novel and specific therapeutic approach for the treatment of patients with gMG. Data shows that rozanolixizumab markedly lowers serum IgG and IgG autoantibody levels in patients with gMG. The completed Phase 2 study MG0002 established supportive evidence of efficacy for the treatment of MG, achieving significant and clinically meaningful improvements to Day 29 in MG-ADL with rozanolixizumab compared with placebo (p=0.036). Repeated administrations of rozanolixizumab were generally and well tolerated, with an acceptable safety profile and in-line with subcutaneous dosing in the Phase 1 program, and the safety profile observed in the proof of concept ITP study.

The most common adverse drug reactions observed after use of rozanolixizumab across indications are headaches and gastrointestinal (GI) disturbances (diarrhea, nausea, vomiting). Potential risks are serious infusion/hypersensitivity reactions, serious infections, and effects on vaccination response. The risks of serious infusion/hypersensitivity and serious infections can be mitigated by careful monitoring, exclusion of at-risk study participants, and appropriate protocol withdrawal and stopping criteria. Additionally, protocol guidance for management of GI disturbances, severe and/or serious headaches, and infusions is also provided as well as expedited reporting requirements of AESM.

More detailed information about the known and expected benefits and risks and reasonably expected adverse events of rozanolixizumab may be found in the current version of the IB.

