MG0002 was a Phase 2, multicenter, randomized, Investigator- and study participant-blind, placebo-controlled, 2-arm repeat dose, treatment sequence study evaluating the safety and efficacy of rozanolixizumab sc (████) in █████ study participants with generalized MG. Marked improvements in patient-reported MG symptoms and disability, as measured by change from Baseline to Day 29 in MG-ADL, were observed following treatment with rozanolixizumab █████ compared with placebo. The least squares (LS) mean (Standard Error [SE]) change from Baseline was █████ for the Rozanolixizumab █████ Group and █████ for the Placebo Group. The difference between treatment groups was █████ (p=████, [████ upper confidence interval (CI): █████]). Smaller but numerical differences in favor of rozanolixizumab █████ vs placebo were observed in reductions from Baseline in QMG on Day 29 with the LS mean (SE) change from Baseline of █████ for the Rozanolixizumab █████ Group and █████ for the Placebo Group. The LS mean (SE) change from Baseline in MG-C score to Day 29 was █████ for the Rozanolixizumab █████ Group and █████ for the Placebo Group. In general, responder rates for QMG score, MG-C score, and MG-ADL score were higher for the rozanolixizumab █████ group than the placebo group. Serum total IgG concentrations and AChR autoantibodies rapidly decreased from Baseline in the rozanolixizumab █████ group in Dosing Period 1 and continued to decline on further dosing with █████ to a mean nadir of █████ for total IgG (████ reduction from Baseline). Overall, repeated administrations of rozanolixizumab at dose levels of █████ and █████ sc have been generally █████ and well tolerated, with an acceptable safety profile. No new safety concerns have been identified to date. The TEAE profile was similar between rozanolixizumab and placebo, except for headaches where increased frequency and severity was observed in the rozanolixizumab-treated study participants.

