Consistent with the mechanism of action of rozanolixizumab, an increased catabolism of IgG will reduce disease-specific autoantibodies with corresponding improvements in clinical signs and symptoms. Two sc treatment arms, equivalent to individual █████ and █████ dosing, have been selected to provide maximal reduction in autoantibody concentration and result in clinically significant improvements in the primary endpoint. A dose of █████ has demonstrated clinical improvements in MG-ADL in study MG0002 (as described above). Additional data from the Phase 2 study in study participants with ITP (TP0001) demonstrated that rozanolixizumab was well tolerated at doses at █████ with further IgG reduction achieved. An individual equivalent dose of █████ has been included to assess if further improvements in MG-ADL (magnitude of response and time to onset of symptom relief) can be achieved at a higher dose level with greater and more rapid IgG reduction.

A population PKPD model that characterizes the dose-exposure-IgG relationship was used to guide, through simulation, the choice of fixed unit doses at each weight bracket that achieved equivalent IgG reductions (mean and █████ prediction interval) to the weight-based (mg/kg) dosing regimens studied previously. These models-based simulations demonstrate that the proposed █████ doses of rozanolixizumab for 6 consecutive weeks are expected to produce mean maximum IgG reductions of █████. These reductions will be achieved rapidly and maintained consistently over the Treatment Period.

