4 STATISTICAL/ANALYTICAL ISSUES

4.1 Adjustments for covariates

The efficacy analyses will be adjusted for the following covariates:

- Baseline MG-ADL score,
- Region (North America, Europe, and Asia [excluding Japan], Japan),
- Stratification factors – MG-specific autoantibodies, including muscle specific kinase [MuSK(+/-)] and acetylcholine receptor [AChR(+/-)], both as binary variables.

In statistical modeling, the stratification factors MuSK(+/-) and AChR(+/-) will be based on the values from MG-specific autoantibody assessment at Baseline. In case Baseline MG-specific autoantibody result is missing (and not resolved after data queries), a post-Baseline measurement may be used. If this is not available, then the historical result will be used in the model; if the historical result is missing as well, the stratification factor from IWRS randomization file will be used to determine values used in the model (i.e., if the stratification is MuSK in IWRS, then

MuSK(+/-) will be imputed as positive, otherwise negative; similarly, if stratification factor is AChR in IWRS, then AChR(+/-) will be imputed as positive, otherwise negative).

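### SAP 4.1 lets a post-Baseline antibody result define the MuSK and AChR covariates ahead of two pre-treatment sources

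*SAP*

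**What the plan says.** SAP 4.1 enters antibody status as two binary variables, which "will be based on the values from MG-specific autoantibody assessment at Baseline". If that result is missing and queries do not resolve it, the order is:

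1. a post-Baseline result first: "a post-Baseline measurement may be used";
2. the historical result, if there is no post-Baseline one;
3. the stratum last: "if the historical result is missing as well, the stratification factor from IWRS randomization file will be used".

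The variables enter the primary MMRM (SAP 8.2.2), the responder model (8.3.1) and the models for the continuous secondary endpoints (8.3.2 to 8.3.6). SAP 4.9.1 applies the same missing-value algorithm to the antibody subgroups.

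On the drug's effect, Protocol 2.3 states that "rozanolixizumab markedly lowers serum IgG and IgG autoantibody levels in patients with gMG". Protocol 4.3 reports from Phase 2 that "Serum total IgG concentrations and AChR autoantibodies rapidly decreased from Baseline", and gives the mechanism: "an increased catabolism of IgG will reduce disease-specific autoantibodies".

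On later testing, a footnote to the Schedule of Activities (Protocol 1.3) has both antibodies tested at Baseline and adds: "All subsequent testing will be limited to the positive antibody".

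**The concern.** A covariate in a randomised comparison should be fixed before treatment starts. If treatment can change it, adjusting for it can move the estimated treatment effect, in a direction set by how the covariate relates to outcome. Here the fallback value is the quantity that the drug is designed to reduce. A participant who was positive before dosing could be entered as negative because the drug worked.

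Two further gaps add to this. The wording is permissive and names neither a visit nor a criterion, which leaves discretion inside the primary model. And later testing follows only the antibody found positive at Baseline, so the documents do not say which antibody is tested, or how the untested one is coded, when the Baseline result is the one that is missing.

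Pre-treatment information should be at hand. Inclusion criterion 3a requires a confirmed positive record at Screening, and randomisation is stratified by antibody type (Protocol 6.3), so the stratum should exist for every randomised participant.

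**Working it through.** The plan states no figure on this point, so there is none to reproduce. The check has two parts.

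**1. Can a scheduled post-Baseline sample be free of drug effect?** In the Schedule of Activities, dosing is at V2, V4, V5, V6, V8 and V9. Antibody samples after V2 are at V5, V8, V10, V12 and V14. Protocol 8.7 has immunological samples taken before the dose. The earliest one, V5 (Day 15), therefore follows the Day 1 and Day 8 doses. On the planned schedule no post-Baseline sample precedes drug effect.

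**2. How far could the estimate move?**

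From SAP 2.4: treatment difference 2.0 (entered as −2, since a fall in MG-ADL is improvement) and SD 3.5.

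Assumed, because the documents give no values:
- share with missing Baseline result, m = 2%, 5%, 10%;
- share of active-arm positives turning negative, f = 10%, 50%, 100%;
- no conversion on placebo;
- share positive, p = 0.9;
- antibody coefficient, g = −2 or +2 points.

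A two-arm ANCOVA with 60 per arm and one antibody covariate was simulated 2,000 times per setting. The true pre-dose status was compared with status taken after dosing in those with a missing Baseline result. Mean shift in the treatment difference, in points:

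| Missing | f = 10% | f = 50% | f = 100% |
|---|---|---|---|
| 2% | 0.003 | 0.016 | 0.031-0.032 |
| 5% | 0.008-0.009 | 0.037-0.039 | 0.071 |
| 10% | 0.016 | 0.070 | 0.120-0.121 |

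With g = −2 the shift favours the drug; with g = +2 it goes against the drug by about the same amount.

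A large-sample formula agrees. Let q = m × f be the share of active-arm positives who are recoded. Then

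shift = g × p × q × R, where R = [p(1−p) + p(1−q)(1−p)] / [p(1−p) + p(1−q)(1−p(1−q))].

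- Top of the range, q = 0.10 × 1 = 0.10: R = (0.09 + 0.081) / (0.09 + 0.81 × 0.19) = 0.171 / 0.2439 = 0.701. Shift = 2 × 0.9 × 0.10 × 0.701 = 0.126.
- Bottom of the range, q = 0.02 × 0.10 = 0.002: R = (0.09 + 0.0898) / (0.09 + 0.8982 × 0.1018) = 0.1798 / 0.1814 = 0.991. Shift = 2 × 0.9 × 0.002 × 0.991 = 0.0036.

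Against the assumed difference of 2.0, the simulated maximum of 0.12 is 0.12 / 2.0 = 6%, and it needs 10% missing with every affected active-arm positive turning negative. This illustrates size only. It is not the stage-wise MMRM with two antibody variables.

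With only pre-treatment sources, treatment cannot affect the covariate and this shift is zero by construction.

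**The case against.** **The trigger is rare.** SAP 3.3 defines Baseline as the last pre-dose value, scheduled or unscheduled, falling back to Screening. SAP 9.2.1 defines the antibody Baseline as the last assessment before first IMP, historical data excluded. The fallback therefore applies only when no pre-dose study assay exists and queries have failed. This stands, and it limits the size.

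**A lower level is not a negative result.** The covariate is binary, and the documents give no conversion rate, assay cut-off or prognostic coefficient. A shift needs a missing Baseline result, conversion and a prognostic covariate together. This stands too.

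**The alternatives are imperfect.** SAP 9.2.1 notes that historical assays came from a different vendor. Historical status may be unknown (SAP 6.2), and entry requires a positive record for only one antibody. The IWRS fallback codes one antibody positive and the other negative, whereas SAP 3.9 adopted two variables in order to capture double-positives. These are reasons for caution about the other sources. They do not justify ranking a sample taken on treatment above a stratum fixed before treatment.

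**Checks are planned.** The primary and continuous secondary analyses are repeated with historical status (SAP 8.2.6 and 8.3.2 to 8.3.6), as are the subgroups (4.9.1). These could reveal a material effect, but they are exploratory or descriptive and the primary model keeps the rule.

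A reader might infer that misclassification would occur only in the active arms. The documents do not support that: rescue IVIg or PEX is open to every arm (Protocol 6.5.4), and the Protocol introduction describes such treatments as aimed at reducing circulating IgG autoantibodies.

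**Conclusion.** The point holds as a minor one. A treatment-affected value can define a covariate in the primary model and the membership of the antibody subgroups, although pre-treatment sources exist. The illustrated shift of about 0.003 to 0.12 MG-ADL points, in either direction, rests wholly on assumed missing and conversion rates, an assumed coefficient and no conversion on placebo. No sample size, power or alpha figure depends on it.

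Two stronger readings are tempting. One is that the primary result would be materially biased; even the extreme setting gives 0.12 points against an assumed effect of 1.5 to 2.0. The other is that the MuSK+ subgroup would be distorted. The documents give no MuSK+ count and no number reclassified, and the subgroup analyses are descriptive, with at least 5 participants required in each level.

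**What to change.** In SAP 4.1 delete the post-Baseline step. The order becomes Baseline assay (last pre-dose study value, as 3.3 and 9.2.1 already define it), historical result, IWRS stratum. SAP 4.9.1 follows by its cross-reference. No separate step for screening or unscheduled pre-dose assays is needed, because the Baseline definition covers them. Moving the post-Baseline step to the end would have the same effect, since the stratum should exist for everyone randomised. Add a count, by arm, of participants whose status came from each source.

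The cost is one sentence and one short table. The small downside is that a few participants would rely on another vendor's assay or, where historical status is unknown, on a stratum that cannot show a double-positive.

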4.2 Handling of dropouts or missing data

4.2.1 Efficacy data

The rules for handling missing data of individual items in the calculation of the QMG, MG-C, MG-ADL, MG Symptom PRO, MGII, and MG-QOL15r scores at a certain visit are described in [Section 13.1](#), [Section 13.2](#), [Section 13.3](#), [Section 13.4](#), [Section 13.5](#) and [Section 13.6](#), respectively.

Imputation methods for missing overall scores (including missing data due to intercurrent events [Section 8.1](#)) for the analyses of primary and secondary endpoints are listed as below. The estimand corresponding to these analyses are described in [Section 8](#).

Efficacy Endpoints	Statistical Analysis Type	Statistical Analysis Methods	Imputation Methods
Primary	Primary	MMRM	Imputation: maximum likelihood estimation
	Sensitivity 1	MMRM	Imputation: maximum likelihood estimation
	Sensitivity 2	MMRM	Imputation: J2R
	Sensitivity 3	MMRM	Imputation: maximum likelihood estimation
	Sensitivity 4	MMRM	Imputation: maximum likelihood estimation
	Supplemental 1	Trimmed Mean using ANCOVA	Imputation: worst score
	Supplemental 2	MMRM	Imputation: maximum likelihood estimation
Secondary (continuous)	Secondary	MMRM	Imputation: maximum likelihood estimation
	Sensitivity	MMRM	Imputation: J2R
	Supplemental	Trimmed Mean using ANCOVA	Imputation: worst score
Secondary (binary)	Secondary	Logistic model	Imputation: NRI

MMRM=mixed model for repeated measures; ANCOVA= analysis of covariance; J2R=Jump to reference; NRI= nonresponse imputation

For other binary efficacy endpoints (e.g. QMG responder), missing data will be imputed using nonresponse imputation (NRI). That is, study participants with missing data at the timepoint of interest, and all timepoints after use of rescue medication will be treated as non-responders.

For ordinal endpoints (EQ-5D-5L, PGI-S, PGI-C), the observed case method will be applied. No further imputation is used.

4.2.2 Dates and times

Partially or completely missing dates may be imputed for the following reasons:

- Classification of AEs as TEAEs;
- Classification of medications as past, prior, or concomitant medications;
- Durations of AEs;

Imputed dates will not be shown in listings. All dates will be displayed as reported in the database.

The following rules will be applied for partially or completely missing start dates:

- If year, month and day are all missing then assign the date of first dose of IMP. If an imputed start date is after the specified end date, then assign January 01 of the year of the end date, or the date of screening if this is later (if the latter imputation results in an end date that is earlier than the start date, then use January 01).
- If month and day are missing, and year is:
 - the same as the year of the first dose of IMP then assign the month-day of first dose of IMP. If the imputed start date is after the specified end date, then assign January 01, or the month-day of screening date if this is later (if the latter imputation results in an end date that is earlier than the start date, then assign January 01);
 - not the same as the year of the first dose of IMP then assign January 01.
- If only day is missing, and month-year is:
 - the same as the month-year of the first dose of IMP then assign the day of first dose of IMP. If the imputed start date is after the specified end date, then assign first day of the month, or the day of screening date if this is later (if the latter imputation results in an end date that is earlier than the start date, then assign first day of the month);
 - not the same as the month-year of the first dose of IMP then assign the first day of the month.

The following rules will be applied for partial stop dates:

- If only the month and year are specified, then use the last day of the month;
- If only the year is specified, then use December 31 of the known year;
- If the stop date is completely unknown, then use discharge date or data cut-off date.

Note: Discharge date refers to the date of the end of study visit for completed study participants or the date of discontinuation for study participants that were withdrawn. For any AEs with known start date after the date of discontinuation, the date of last contact will be used as the discharge date. For study participants still ongoing in the study at the time of the data cut-off, and for whom no discharge date is available, the date of the data cut-off will be used instead of the discharge date.

Any medication with a start date on the first dosing date and time unknown, will be assumed to be concomitant.

Imputed AE dates will be used for the calculation of duration of AEs as described in [Table 4-1](#).

Table 4-1: Calculation rules for duration of AEs

Data availability	Onset date	Outcome date	Calculation rules
Complete data	D1	D2	Duration = D2 – D1 + 1 day
Start date partially or completely missing	--	D2	Duration ≤ D2 – D0 + 1 day Notes: D0 is imputed start date per above rules.
End date partially or completely missing	D1	--	For ongoing AE: Duration ≥ D3 – D1 day For resolved AE: Duration ≤ D3 – D1 day Notes: D3 is imputed end date per above rules.
Start and end date partially or completely missing	--	--	For ongoing AE: Duration ≥ D3 – D0 day For resolved AE: Duration ≤ D3 – D0 day Notes: D0 is imputed start date and D3 is imputed end date per above rules.

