6.5 Concomitant Medication(s)/Treatment(s)

6.5.1 Permitted concomitant treatments (medications and therapies)

All concomitant treatments permitted during the study are presented in Table 6-1.

Any violation of the permitted treatment criteria would lead to prohibited treatment and should be discussed with the Investigator, sponsor and Medical Monitor.

Table 6-1: Permitted Concomitant Treatments

Permitted Medications	Dose	Comment
Oral Corticosteroids (eg, prednisolone)	No specific requirements	Stable for █████ prior to Baseline ^a
Methotrexate	≤30mg/week	Treated for previous █████ and on stable dose for █████ prior to Baseline ^a
Mycophenolate mofetil	≤3g/day	Treated for previous █████ and on stable dose for █████ prior to Baseline ^a
Cyclosporine ^b	≤5mg/kg/day for unmodified ≤4mg/kg/day for modified (microemulsion)	Treated for previous █████ and on stable dose for █████ prior to Baseline ^a
Azathioprine	≤3mg/kg/day	Treated for previous █████ and on stable dose for █████ prior to Baseline ^a
Cholinesterase inhibitors	≤600mg Pyridostigmine/day	Stable dose not required – dose █████ of efficacy outcomes

Permitted Medications	Dose	Comment
Tacrolimus ^c	≤5mg/day	Treated for previous [REDACTED] and on stable dose for [REDACTED] prior to Baseline ^a

^a Must also be stable for duration of study.

^b Doses higher than listed are permissible if trough level is ≤300ng/mL.

^c If the total daily weight-based dose is >5mg, then a plasma trough level should be checked to ensure study participant is not above the recommended therapeutic range.

The use of medicinal cannabidiols and medicinal marijuana (prescribed by a physician) is also permitted. When applicable, the study participant must be on a stable dose of cannabidiols and/or medicinal marijuana for [REDACTED] prior to Screening, and remain stable for the duration of the study.

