4.9 Examination of subgroups

4.9.1 General subgroups

The primary and continuous secondary efficacy endpoints will be evaluated for subgroups of interest including:

- Age (18 - <65 years, ≥ 65 years)
- Age (18 - <65, 65 - <85, ≥ 85 years)
- Sex (male, female)
- Region (North America, Europe, and Asia [excluding Japan], Japan)
- Stratification factors – MG-specific autoantibodies, MuSK(+/-) and AChR(+/-)

Note: The stratification factors MuSK(+/-) and AChR(+/-) in the subgroup analysis will be based on the values from MG-specific autoantibody assessment taken at Baseline, using the same algorithm for missing values as specified in Section 4.1. Historical MuSK (+/non +) and historical AChR(+/non +) will also be examined in the subgroup analysis, in this case, Baseline MuSK(+/-) and Baseline AChR(+/-) will be replaced by Historical MuSK (+/non +) and historical AChR (+/non +).

The MG-ADL scores and change from Baseline will be summarized in the five subgroups as above and additional subgroups as follow:

- Duration of disease at Baseline (<median, \geq median)

- MGFA disease class at Baseline
- Thymectomy at Baseline (yes, no)
- Baseline MG-ADL category (<5, ≥5).

The following subgroups of MG baseline medications will be derived in the analysis datasets and used for ad-hoc reporting purposes. See Section 6.4.3 for definition of MG baseline medications.

- Baseline Oral steroid (yes, no)
- Baseline Immunosuppressants other than oral steroid (yes, no)
- Baseline Cholinesterase inhibitor (yes, no)

All subgroup analyses will be descriptive; no statistical testing of treatment-by-subgroup interactions nor statistical testing of treatment effects within subgroups will be carried out. No subgroup analysis is planned for safety variables.

Forest plots will be provided to summarize subgroup analysis.

Subgroup analyses will only be performed for subgroups where there are at least 5 study participants in each subgroup level, otherwise it will not be performed.

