6.4.1 Categories of prior and concomitant medications

Medications will be classified as follow based on imputed start and stop dates & times as outlined in [Section 4.2.2](#).

- **Past** medications will include any medications that started and stopped before the first administration of IMP.
- **Prior** medications will include any medications that started before the first administration of IMP.
- **Baseline** medications will include any medications that started prior to dosing and continued after (classified as prior and concomitant medications).
- **Concomitant** medications will include any medications that have been taken at least once after the first administration of IMP during the Treatment and/or Observation Period.
- **Concomitant Only** medications will include any medication that started after the first administration of IMP and continues during the Treatment and/or Observation Period.

Table 6–1: Concomitant Medications Classification

Medication Started	Medication finished	Classification
Before 1 st Dose IMP	Before 1 st Dose IMP	Past
Before 1 st Dose IMP	Any time	Prior
Before 1 st Dose IMP	After 1 st Dose IMP	Baseline (= prior and concomitant)
Any time	After 1 st Dose IMP	Concomitant
After 1 st Dose IMP	After 1 st Dose IMP	Concomitant Only

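### The start-date rule built for adverse events is also used for medications, so an ongoing background drug with an unknown start date drops out of the Prior and Baseline medication tables

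*SAP*

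**What the plan says.** SAP 4.2.2 lists the reasons for imputing dates. Two of them are "Classification of AEs as TEAEs" and "Classification of medications as past, prior, or concomitant medications". One set of start-date rules follows, with no separate branch for medications:

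- Wholly missing start: "If year, month and day are all missing then assign the date of first dose of IMP".
- Only the year known, and it is the first-dose year, or only the month and year known, and they are those of first dose: the first-dose date again.
- Any other recorded year or month: the first day of that year or month.
- A fallback for records whose known end date precedes the imputed start. For a wholly missing date it reads "If an imputed start date is after the specified end date, then assign January 01 of the year of the end date", or the screening date if that is later and still fits. The partial-date branches have an equivalent.
- A wholly unknown stop date becomes the discharge or data cut-off date.

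The section then adds a tie-break: "Any medication with a start date on the first dosing date and time unknown, will be assumed to be concomitant".

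SAP 6.4.1 classifies medications from these imputed dates. Prior requires a start before the first administration. The Baseline class reads "medications will include any medications that started prior to dosing and continued after". SAP 6.4 tabulates these classes on the Randomized Set.

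Protocol 6.5.1 permits oral corticosteroids and the listed immunosuppressants only if they were stable for a stated period before Baseline, with the footnote "Must also be stable for duration of study". Cholinesterase inhibitors are exempt from the stable-dose requirement.

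**The concern.** The same default works in opposite directions for the two kinds of record. For an adverse event of unknown onset, a start at first dose is the conservative assumption. For a background steroid or immunosuppressant, it assigns a start date that a participant who met Protocol 6.5.1 could not have, since the drug had to be in place before Baseline.

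At stake is the description of the population. The Prior and Baseline medication tables show what treatment participants brought into the trial, and they would undercount it.

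Two further outputs may be touched. SAP 6.2 summarises MG medication by reference to 6.4.3, and SAP 4.9.1 says: "The following subgroups of MG baseline medications will be derived in the analysis datasets and used for ad-hoc reporting purposes". Those flags are oral steroid, other immunosuppressant and cholinesterase inhibitor, each yes or no. If they use the 6.4.1 meaning of Baseline, some users become non-users.

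**Working it through.** The plan states no figure for this point, so there is none to reproduce. The check applies the start-date rules and tie-break of SAP 4.2.2 and the classes of SAP 6.4.1 to ten test records. The dates are illustrative: screening 25 Aug 2020, first dose 15 Sep 2020, discharge 22 Dec 2020. Ongoing records take the discharge date as stop date.

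| Recorded start | Stop | Imputed start | Classes met |
|---|---|---|---|
| Wholly missing | Ongoing | 15 Sep 2020 | Concomitant |
| Wholly missing | 20 Oct 2020 | 15 Sep 2020 | Concomitant |
| Wholly missing | 5 Sep 2020 | 25 Aug 2020 | Past, Prior |
| Wholly missing | 1 Jun 2020 | 1 Jan 2020 | Past, Prior |
| Wholly missing | 1 Jun 2019 | 1 Jan 2019 | Past, Prior |
| 2020 | Ongoing | 15 Sep 2020 | Concomitant |
| Sep 2020 | Ongoing | 15 Sep 2020 | Concomitant |
| Mar 2020 | Ongoing | 1 Mar 2020 | Prior, Baseline, Concomitant |
| 2016 | Ongoing | 1 Jan 2016 | Prior, Baseline, Concomitant |
| 2 Apr 2016 | Ongoing | 2 Apr 2016 | Prior, Baseline, Concomitant |

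Four of the ten patterns lose Prior and Baseline status: the two wholly missing starts with use at or after first dose, and the two partial dates that overlap first dose. In each, the imputed start equals the first-dose date, which is not before first dose, and the tie-break makes the drug concomitant. The three undated drugs that stopped before dosing are rescued by the fallback. The last three rows are classified correctly.

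The two partial-date rows are errors only if the drug really began before dosing. A record known only to the first-dose year or month could be a true on-study start.

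**Size.** The documents give no rate of missing medication start dates. As an assumption, let a share p of participants have at least one affected record. The number affected is N × p, with N = 150 to 240 from SAP 2.4:

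- p = 1%: 150 × 0.01 = 1.5; 240 × 0.01 = 2.4
- p = 5%: 7.5; 12
- p = 10%: 15; 24
- p = 20%: 150 × 0.20 = 30; 240 × 0.20 = 48

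The range of about 2 to 48 participants shows scale only. It is not an estimate.

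**Route to the MG-specific outputs.** SAP 6.4.3 defines MG Baseline medication by indication and ATC code and states no date test. If Baseline there carries the 6.4.1 definition, the four patterns above also count as non-use in the 6.2 summary and the 4.9.1 flags. If it does not, 6.4.3 has no timing test at all, and an MG drug begun on study would qualify.

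**The case against.** The strongest reply is that the gap is narrow and the outputs are descriptive. Long-standing drugs usually have at least a year recorded, and any year before the first-dose year is handled correctly. Protocol 6.5.1 makes sites establish prior treatment or dose stability for steroids and immunosuppressants, so a wholly unknown start should be uncommon for them. The affected drug is still reported as Concomitant. All of this stands and limits the size of the problem, but it does not make the imputed class right.

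A reader might also infer more than the documents support:

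- **That every undated or partly dated MG record is misclassified.** The fallback keeps drugs stopped before dosing in Past and Prior, and some partial dates may be true on-study starts.
- **That the Concomitant Only table would show new MG drugs after dosing.** That class requires a start after the first administration, and the tie-break assigns a same-day start with unknown time to Concomitant. The SAP leaves the same-day case unclear for Concomitant Only; it does not place the record there.
- **That the records would count as protocol deviations.** SAP 3.4 identifies important deviations through separate criteria and data review and does not mention imputed dates. Under SAP 4.2.2 and 6.4, listings show dates as reported.
- **That the MG subgroups are certainly wrong.** The effect depends on how 6.4.3 is read. The flags are for ad-hoc use, and SAP 4.9.1 makes all subgroup analyses descriptive.

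The remedy has a cost as well: treating unknown starts as before dosing could put an occasional true on-study start into Baseline.

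**Conclusion.** The point holds for a medication still taken at or after first dose whose start date is wholly missing, or known only to the first-dose year or month. The stated rules exclude it from Prior and Baseline, and nothing elsewhere in either document restores it. This is a rule that gives a wrong answer for background therapy, not a missing detail.

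The consequence is an undercount of background MG drugs in the descriptive Prior and Baseline tables. The 6.2 summary and the three ad-hoc flags are affected only on the reading that 6.4.3 uses the 6.4.1 definition. The efficacy models, their covariates (SAP 4.1), the identification of rescue therapy (SAP 8.4.1, from the CRF response or procedure record) and error control do not depend on these dates. The count of affected records cannot be derived from the documents. The correction is worth making because it is cheap, not because any inference is at risk.

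**What to change.** In SAP 4.2.2, limit the first-dose default to adverse events and add a rule for medications:

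- **Wholly missing start, no evidence of an on-study start:** treat the drug as started before first dose. Class it as Past if it stopped before dosing, and otherwise as Baseline (so both Prior and Concomitant).
- **Partial date overlapping the first-dose year or month:** use the earliest date consistent with the recorded part, unless the record shows an on-study start. In the examples above, 2020 becomes 1 Jan 2020 and Sep 2020 becomes 1 Sep 2020, and both ongoing drugs are then Prior, Baseline and Concomitant.

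In SAP 6.4.3, state that Baseline uses the 6.4.1 definition.

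The cost is a few sentences and a small programming change. The downside is that an occasional true on-study start with an unknown date would be counted as Baseline, although it would still appear as Concomitant.
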